Patients: intentions vs. actual decisions for mammography	‘Post’: Examine whether patient intentions for mammography agree with whether mammography is scheduled or not (using chart abstraction)
Patients & Clinicians: Agreement in intentions	‘Post’ for patients and providers: degree of agreement on scores 1-15
Patients & Clinicians: life expectancy wishes	‘post’ for patients and providers: tabulate responses for willingness to discuss

8.5 Primary Outcomes for Aim 1.2: We will focus on the primary outcomes of intentions for mammography and acceptability/ feasibility. We use the sign rank and exact McNemar’s testing to compare the ‘pre’ vs. ‘post’ results for the score for intention and proportion who indicate ‘yes’, respectively. To account for clustering by clinician, we will utilize random effects models if parametric assumptions hold, or alternatively using bootstrap resampling techniques to compute 95% confidence intervals for the change in intention. We anticipate a low number of missed surveys because of the CRC follow-up planned by phone if necessary. If a patient is missed for her ‘pre’ test survey, we will replace her to ensure enrollment of 45 with ‘pre’ and ‘post’ surveys. We will compare characteristics of those with missing surveys and missing questions to those with complete surveys to assess for any notable differences. For feasibility, we will declare the tool feasible if $\geq 75\%$ of patients and physicians report usefulness of the tool.

At the conclusion of this arm, we will have preliminary data on how the communication tool impacted care, its feasibility, and about multiple exploratory, secondary endpoints. If we have difficulties with recruitment of patients or clinicians for this project, we will contact additional clinicians and patients to reach our desired accrual goals. Given the high volume of breast cancer patients and clinicians in our system, we anticipate that accrual will occur with ease.

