- 9.3 Survey Instruments. The draft 'pre'/'post' patient surveys and a post-visit clinician survey (all three draft surveys) are in Appendix D. Surveys contain closed-ended questions (except for solicited comments at the end) and are adapted from [name] prior, validated surveys conducted before and after the use of a decision aid for screening mammography in older women.⁶⁶ We will ask about demographics, health literacy and numeracy ('pre' patient), mammography intentions ('pre' and 'post' patient), mammography knowledge ('pre' and 'post' patient), anxiety about recurrence ('pre' patient), acceptability of the communication tool ('pre' patient and clinician), comfort level and interest in discussions about life expectancy ('pre' and 'post' patient and clinician), decisional

PROTOCOL TITLE:

conflict ('pre' and 'post' patient), preferences for a paper/online tool ('post' patient and clinician), and time added to appointments ('post' clinician).

10.0 Data and Specimen Banking – there is no specimen banking as part of this protocol

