13. I feel sure about what to choose in terms of whether or not to get a mammogram.

				
Strongly Agree	Agree	Not sure	Disagree	Strongly Disagree

14. The decision whether or not to get a mammogram is easy for me to make.

				
Strongly Agree	Agree	Not sure	Disagree	Strongly Disagree

15. I feel I have made an informed choice whether or not to get a mammogram.

				
Strongly Agree	Agree	Not sure	Disagree	Strongly Disagree

PROTOCOL TITLE:

16. My decision about whether or not to get a mammogram shows what is important to me

- | | | | | |
|--------------------------|--------------------------|--------------------------|--------------------------|--------------------------|
|  |  |  |  |  |
| Strongly
Agree | Agree | Not sure | Disagree | Strongly
Disagree |

17. I expect to stick with my decision whether or not to get a mammogram

- | | | | | |
|--------------------------|--------------------------|--------------------------|--------------------------|--------------------------|
|  |  |  |  |  |
| Strongly
Agree | Agree | Not sure | Disagree | Strongly
Disagree |

18. I am satisfied with my decision whether or not to get a mammogram.

- | | | | | |
|--------------------------|--------------------------|--------------------------|--------------------------|--------------------------|
|  |  |  |  |  |
| Strongly
Agree | Agree | Not sure | Disagree | Strongly
Disagree |

19. Did your health care provider discuss your life expectancy with you today?

- Yes
- No
- Don't know

20. If yes, how did this make you feel? You can check as many answers as you think apply:

- Comfortable
- Uncomfortable
- Informed
- Sad
- Content/Happy
- Scared
- Anxious
- Calm
- Interested
- Uninterested
- Other _____

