****Post-visit Clinician Questionnaire****

Thank you for agreeing to participate in this study. We are going to ask you some questions relating to this particular visit with the patient. All of your answers will be kept confidential, will not be linked to your name for future use, and are for informational purposes only as we try to understand how helpful this tool was in your discussions with patients. Please answer openly and honestly and you can skip any question you prefer not to answer

Study ID _____

Date: _____

Intentions for mammography

1. What did you recommend in terms of mammograms for this patient?

- Continue having mammograms
- Get another mammogram but consider stopping after that
- It is the patient's choice
- To not get a mammogram now but reconsider later
- To stop getting mammograms
- Did not discuss mammograms
- Other: _____

2. Before the visit, what did you think you would recommend?

- Continue having mammograms
- Get another mammogram but consider stopping after that
- It is the patient's choice
- To not get a mammogram now but reconsider later
- To stop getting mammograms
- I did not think I would discuss mammograms
- Other: _____

3. During the visit today, did you discuss any of the following (circle each answer):

- | | | | |
|--|-----|----|----------|
| • Pros of mammograms? | Yes | No | Not sure |
| • Cons of mammograms? | Yes | No | Not sure |
| • The patients individual risk of in-breast, pre-cancer or invasive cancer events? | Yes | No | Not sure |
| • Family history? | Yes | No | Not sure |
| • Life expectancy? | Yes | No | Not sure |

PROTOCOL TITLE:

- Any other relevant discussion points you discussed?
-

3A. If yes to discussing life expectancy, how did this go? Check any that apply:

- Helpful to patient
- Helpful to me
- It was uncomfortable
- It was comfortable
- Made decision-making easier for mammogram
- Made decision-making harder for mammogram
- Neutral effect on decision-making
- Other _____

3B. If no to discussing life expectancy above, why not? Check any that apply

- It didn't come up
- I was uncomfortable talking about it
- Patient did not want to discuss it
- Patient was anxious
- Patient healthy so I didn't think it was important
- I didn't have time
- I didn't think it was important for this discussion

Questions about the Communication Sheet (with regard to its use during this visit with the patient)

4. The length of the communication sheet was

- | | | | | | |

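### The life expectancy wishes outcome is defined as post-visit willingness, but neither post-visit form asks about willingness directly, so it cannot be tabulated for all patients and providers as defined

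*Protocol*

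**What the plan says.** The last row of Table 2 in protocol Section 8.4 gives life expectancy wishes as a secondary outcome for patients and clinicians. The whole definition is "post’ for patients and providers: tabulate responses for willingness to discuss".

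Section 9.3, which describes the surveys, says that they cover "comfort level and interest in discussions about life expectancy ('pre' and 'post' patient and clinician". It lists three forms: a pre and a post form for patients, and one post-visit form for clinicians. It calls all three drafts.

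Appendix D gives the forms:

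- **Post-visit patient form.** Item 19 asks "Did your health care provider discuss your life expectancy with you today", with yes, no and don't know as answers. Item 20 follows: "If yes, how did this make you feel? You can check as many answers as you think apply".
- **Post-visit clinician form.** Item 3 has a line on whether life expectancy was discussed (yes, no or not sure). Two conditional items follow: "3A. If yes to discussing life expectancy, how did this go? Check any that apply" and "3B. If no to discussing life expectancy above, why not? Check any that apply".

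The SAP says that both patient surveys covered experiences of, and comfort with, life expectancy discussions. It does not mention willingness or wishes.

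**The concern.** Willingness to have a discussion is an attitude that every respondent holds, whether or not the discussion took place. The post-visit items record something else: whether the topic came up, and then either how it went or why it did not come up. The row name and the items do not match.

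The risk is in reporting. If the row is filled from item 20, the table will show reactions among women whose visit included the topic, under a label that implies the wishes of all women enrolled. Under Section 5.3, clinicians use the tool as they see fit and without specific instructions, so the study does not control who reaches item 20.

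The topic matters to this project. Section 2.5 names the incorporation of life expectancy into the decision as a key innovation, and Section 2.7 says the study will supply preliminary data for a randomized trial. A designer of that trial would want to know what share of women, and of their clinicians, are willing to have this conversation.

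**Working it through.** The plan states no figure for this outcome and none can be recomputed. The check compares the definition with the forms, item by item.

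**Step 1. What the definition needs.** It needs a response on willingness, collected after the visit, from patients and from providers. The patient denominator is 45 (Section 4.1). Under Section 5.3, clinicians complete one survey per enrolled patient, so there are up to 45 clinician forms.

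**Step 2. Post-visit patient form, items 1 to 54.**

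| Answer to item 19 | Next life expectancy item | Own willingness recorded? |
|---|---|---|
| Yes | Item 20, feelings | No |
| No | None | No |
| Don't know | None | No |

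Two items concern life expectancy, and none asks about willingness. Item 20 does have tick boxes for being interested or uninterested. These are among the reactions to a discussion that has already happened and are offered only after a yes to item 19, so they do not measure willingness across the sample.

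**Step 3. Post-visit clinician form, items 1 to 12 with 3A and 3B.**

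| Answer to item 3, life expectancy line | Next item | What it records |
|---|---|---|
| Yes | 3A | Helpfulness, comfort or discomfort, effect on the decision |
| No | 3B | Reasons, including the clinician's own discomfort and, as the clinician saw it, the patient's reluctance or anxiety |
| Not sure | None | Nothing further |

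Three items concern life expectancy, and none asks about willingness directly. Item 3B comes closest, but it applies only to visits without the discussion, and it gives the patient's view second-hand.

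**Step 4. Section 9.3 against the forms.** Section 9.3 promises both comfort and interest. Comfort is measured after the visit, conditionally, through options in items 20, 3A and 3B. Interest has no item of its own on either post-visit form.

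**Step 5. Denominators the forms can support.** Ignoring skipped questions:

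- Patients: item 19 yes + no + don't know = 45. Item 20 has a denominator equal to the number of yes answers.
- Clinician forms: item 3 yes + no + not sure = number of forms returned. Item 3A has the yes count as its denominator and item 3B the no count.
- Own post-visit willingness, patients: 0 items, hence 0 of 45.
- Direct clinician willingness: 0 items. There is a partial proxy from 3B in visits without the discussion, and some information on comfort from 3A in visits with it.

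**Step 6. Could the pre-visit form supply it?** Items 31 to 36 of the baseline questionnaire are not visible in the text available for this review, which goes from item 30 to item 37. Section 9.3 places life expectancy questions on the pre form, so these items may record wishes. Even so, Table 2 specifies post-visit data, and there is no clinician pre survey.

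**The case against.** The strongest reply has four parts.

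1. **The clinician form does carry relevant information.** Item 3B goes to clinicians who did not have the discussion. It records their own discomfort and their perception that the patient was unwilling. This stands. A reader might infer that clinicians supply nothing on willingness, or that every question about feelings is limited to visits with a discussion. The form supports neither reading. What it offers is a conditional proxy, short of a willingness measure for every visit.

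2. **Wishes may be recorded at baseline.** This stands as a possibility, because the baseline items in question could not be read. A reader might infer that the study never asks women whether they want this discussion, and the documents do not allow that conclusion. The Aim 1.1 interview script in Appendix C also asks whether patients would be interested in hearing life expectancy information, though of a separate sample. Neither source supplies what Table 2 specifies for Aim 1.2.

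3. **The SAP already speaks of experience and comfort, and no document plans to report item 20 as wishes.** Both statements are correct. The SAP wording is close to what the post-visit items can deliver. But the Table 2 definition remains in the protocol, and the SAP neither withdraws it nor assigns items to it.

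4. **This is one descriptive row in a 45-patient pilot.** Section 8.5 calls the secondary endpoints exploratory, and no test or decision rule depends on this one. That limits the weight of the point but does not remove the mismatch.

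**Conclusion.** A stated secondary outcome has no item that measures it directly. Post-visit willingness can be tabulated for 0 of 45 patients from their own answers. For clinicians it can be approached only through the reasons in 3B, in visits without the discussion, with some information on comfort from 3A. A clinician who answers not sure to item 3 contributes nothing further. The outcome cannot be tabulated for all patients and providers as defined. Item 20 describes only women who had the discussion and should not be presented as wishes.

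Two stronger conclusions are tempting. A reader might infer that using item 20 would overstate willingness because the least willing women drop out of it. The direction is not established: several 3B options, such as lack of time, the topic not arising, or the patient being healthy, have nothing to do with reluctance. A reader might also want the size of the item 20 subset, but the documents give no figure for how often life expectancy will be raised.

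The conclusion rests on both post-visit forms being complete as printed in Appendix D. It does not depend on the content of baseline items 31 to 36. Sample size, power and alpha are not affected.

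**What to change.** **If the forms can still be changed** (Section 9.3 calls them drafts), add one unconditional item to each post-visit form:

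- Patient: *Would you want your health care provider to talk about your life expectancy when you decide about mammograms?* (yes / no / not sure)
- Clinician: *How willing would you be to discuss life expectancy with this patient?*

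Tabulate both over all respondents, and keep items 19/20 and 3/3A/3B as a description of what happened at the visit. The cost is one question on each of two forms.

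**If the forms are fixed** (the SAP is written in the past tense, so data may already have been collected), reword the Table 2 row as experience of life expectancy discussion. Name items 19/20 and 3/3A/3B as its sources and give the denominator for each conditional item, including the count answering don't know or not sure. If a baseline item does measure wishes, cite it in the row and label it pre-visit. Make no post-visit claim about willingness, and bring the sentence in Section 9.3 into line. The cost is one reworded row and one sentence.

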4.0 Study-Wide Number of Subjects*

4.1 For Aim 1.1, we will recruit up to 30 patients and up to 48 providers for the qualitative focus group/interview component, and 5-10 patients for the cognitive interviewing of the tool. For Aim 1.2, we will recruit 45 patients and the providers taking care of those patients.

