
- 5.2 Procedures for recruiting focus groups - Providers (Aim 1.1). [name] will email her colleagues at Brigham and Women's and DFCI to recruit them for a 60- minute focus group discussion, aimed to occur at a regular weekly/monthly meeting for a particular PCP or medical oncology practice. We will provide beverages and snacks for the meeting. We will visit the practice at BWH or DFCI to conduct the focus groups and any virtual focus groups will take place by phone via webex. [name] will also reach out to her broad network of physicians outside of DFCI to recruit oncologists from around the country for the virtual focus group (which will occur via

PROTOCOL TITLE:

webex/phone). [name] (who is experienced in leading clinician-based focus groups) will lead all clinician focus groups. All discussions will be recorded and professionally transcribed. At the start of the clinician focus groups, verbal consent from each participant will be obtained and providers will be provided a written copy of the verbal consent in person or via email. We do not intend to register providers in Oncpro.

- 5.3 Procedures for recruiting providers and patients for the tool intervention (Aim 1.2)
We will then test the communication tool at DFCI, DFCI at South Shore Hospital , and DFCI at St. Elizabeth's breast medical oncology practices. [name] will recruit 10-12 medical oncology colleagues who each agree to test the communication tool in ≤5 of their older patients over a 4-6-week period.

Before the visit. To identify mammography-eligible patients with low-to-average risk for in-breast recurrences, the dedicated CRC will scan participating clinician schedules daily over a 4-6-week period at DFCI/St. E's/South Shore Hospital for breast cancer patients with stage 0-II breast cancer who have completed any chemotherapy, surgery, and/or radiation ≥12 months prior and who are aged ≥75 and who had breast-conserving surgery. If a patient meets criteria for possible enrollment, the CRC will email the clinician (Appendix H) to confirm that mammography would typically be discussed at this visit and to ask permission to offer the study to the patient.

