- 8.4 Outcomes and Analyses for Aim 1.2. The outcomes of interest are shown in Table 2 below and have been adapted from [name] prior survey study testing a decision aid for screening mammography for older women.⁶⁶ We will focus on a primary outcome of intentions for mammography and will examine how various factors (race, health literacy, numeracy, anxiety, life expectancy) impact intentions. We use the sign rank and exact McNemar’s testing to compare the ‘pre’ vs. ‘post’ results for the continuous score for intention and proportion who indicate ‘yes’, respectively. To account for clustering by clinician, we will utilize random effects models if parametric assumptions hold, or alternatively using bootstrap resampling techniques to compute 95% confidence intervals for the change in intention. We anticipate a low number of missed surveys because of the CRC follow-up planned by phone, mail, or email if necessary. If a patient is missed for her ‘pre’ test survey, we will replace her to ensure enrollment of 45 with ‘pre’ and ‘post’ surveys. We will compare characteristics of those with missing surveys and missing questions to those with complete surveys to assess for any notable differences.

Table 2. Outcomes of Interest for Aim 1.2	
Outcome(s) of Interest	Outcome definitions, planned analyses

PROTOCOL TITLE:

Primary Outcomes: Patients: Frequency of change in intentions for mammography in the next year	15 point validated scale to assess ‘pre’ vs ‘post’ survey responses where scores 1-5 = yes to having mammography, 6-10 = unsure, 11-15 = no for mammography. We will use a continuous outcome of 1-15. ^{66,79}
Patients & Clinicians: Acceptability & Feasibility	Length, clarity; tabulate responses ⁸⁰ ; 75% report the tool is useful
Secondary Outcomes:	
Clinicians: satisfaction, time added/removed	Tabulate responses, prepare descriptive analyses
Patients: preferred decision-making role	‘Pre’ survey: Examine preferences for active, shared, passive decision-making ⁸¹
Patients: Decisional conflict	‘Pre’ vs. ‘Post’ survey: 16 item scale, Calculate total and sub-scale responses. Scores range 1-100, lower scores indicating higher quality decision-making ^{82,83}
Patients: Knowledge about mammography	Number of correct (10) knowledge questions on ‘pre’ vs. ‘post’ surveys. ^{66,84,85}

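### The primary tests of change in intention ignore clustering by clinician, and the clustered 95% interval is left to an undefined choice of method; the simplest bootstrap reading would cover about 90% with 10-12 clinicians

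*Protocol*

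**What the plan says.** Protocol 4.1 sets the size of the pilot: "For Aim 1.2, we will recruit 45 patients and the providers taking care of those patients". Section 5.3 gives the cluster structure: the study lead "will recruit 10-12 medical oncology colleagues who each agree to test the communication tool in ≤5 of their older patients". Section 8.5 leaves the number of clinicians open if accrual is slow: "we will contact additional clinicians and patients to reach our desired accrual goals".

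Table 2 defines the outcome as the intention score before and after the visit: "We will use a continuous outcome of 1-15". For inference, 8.4 and 8.5 say "We use the sign rank and exact McNemar’s testing to compare the" pre and post results, signed-rank for the score and McNemar for the proportion answering yes. The next sentence turns to clustering by clinician and offers "random effects models if parametric assumptions hold, or alternatively using bootstrap resampling techniques to compute 95% confidence intervals for the change in intention".

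The SAP reports descriptive analyses and t-tests of the change in decisional conflict. It mentions no random effects model, bootstrap or clustered interval, and no test of the change in intention.

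**The concern.** There are three gaps.

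1. The plan recognises that patients of the same clinician may respond alike, which is natural when the clinician conducts the visit at which the tool is discussed. Yet the two tests that yield the primary p-values treat all 45 patients as independent. The p-value and the interval therefore rest on different assumptions and can disagree.
2. The choice between model and bootstrap depends on a look at the outcome data, with no test, threshold or blinded review defined. The bootstrap branch is a live possibility. The score is bounded, and Protocol 2.6 reports that nearly 80% of survivors aged 65 or older had a mammogram in the last year, so many baseline answers may sit at the low (will get) end.
3. If the bootstrap branch is taken, the text does not say what is resampled or how the interval is formed. With so few clusters, that choice decides whether the nominal 95% is attained.

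Protocol 2.7 says the study will supply preliminary data for a randomized trial, so a poorly calibrated interval would carry into its planning.

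**Working it through.** The documents give no power, SD, ICC or interval width for Aim 1.2, so there is no planned figure to reproduce. The check is whether the nominal 95% and 5% levels would be attained.

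**Inputs from the protocol.** n = 45 patients; k = 10 to 12 clinicians with at most 5 patients each; mean cluster size m = 45/12 = 3.75 to 45/10 = 4.5.

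**Assumptions.** ICC of the change score 0, 0.05, 0.10 or 0.20; change either normal or a skewed integer distribution with many zeros; two-sided 5% level.

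**Step 1. Percentile bootstrap over clinicians.** For k equal clusters, the half-width is about 1.96 × √((k−1)/k) standard errors, where a t interval uses t(k−1). Approximate coverage is 2F(1.96√((k−1)/k)) − 1, with F the t(k−1) distribution function.

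| k | 1.96√((k−1)/k) | t(k−1), 97.5% | Coverage | Width ratio to t |
|---|---|---|---|---|
| 10 | 1.859 | 2.262 | 90.4% | 0.822 |
| 11 | 1.869 | 2.228 | 90.9% | 0.839 |
| 12 | 1.877 | 2.201 | 91.3% | 0.853 |
| 15 | 1.894 | 2.145 | 92.1% | 0.883 |
| 20 | 1.910 | 2.093 | 92.9% | 0.913 |

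The ICC does not enter the formula, so the shortfall is present even at ICC 0. Simulation (2,000 trials per setting, 999 resamples) gave 89.2-92.2% with normal change and 86.6-91.1% with skewed change.

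**Step 2. Other methods the wording would allow, or that might replace it.**

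| Method | Normal change | Skewed change |
|---|---|---|
| Cluster bootstrap-t | 94.2-95.9% | 92.6-95.8% |
| Cluster-robust t(k−1) | 94.0-96.1% | 90.6-93.6% |
| Random intercept (REML), Wald z | 91.9-96.0% | not run |
| Random intercept (REML), t(k−1) | 95.7-98.0% | not run |

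Kenward-Roger degrees of freedom were not simulated; the t(k−1) row is the nearest check. A plain t interval on clinician means behaves like the cluster-robust t: 94-96% with normal change, about 90-94% with skewed change.

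**Step 3. Unadjusted test.** The design effect is 1 + (m−1) × ICC. A test that ignores it has approximate type I error 2[1 − Φ(1.96/√DE)]. At m = 45/11 = 4.09:

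- ICC 0: DE = 1, type I error 5.0%.
- ICC 0.05: DE = 1 + 3.09 × 0.05 = 1.155, 1.96/√1.155 = 1.824, type I error 6.8%.
- ICC 0.10: DE = 1.309, 1.96/√1.309 = 1.713, type I error 8.7%.
- ICC 0.20: DE = 1.618, 1.96/√1.618 = 1.541, type I error 12.3%.

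Simulation of the signed-rank test with normal change and no true effect agrees: near 5% at ICC 0, about 8-10% at 0.10, and 10-13% at 0.20. The exact McNemar test was not simulated. It has the same lack of adjustment, but no size is claimed for it here.

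**The case against.** The strongest reply is that the protocol never names a percentile bootstrap. A cluster bootstrap-t fits the same words and covers about 93-96% in Step 2. That stands, so the 90% figure is conditional on one variant.

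A reader might also infer that the trial's error bars are too narrow. The documents do not support that: they state no interval and no width. Nor do they support treating a patient-level bootstrap as the plan, because the sentence says its purpose is to account for clustering and resampling patients would defeat it.

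Other points stand in part. Clinicians are not capped at 12, although by Step 1 the percentile interval still falls short at 15 or 20. The type I error figures depend on an ICC that the documents do not give, and they shrink towards 5% as it falls. Aim 1.2 is an uncontrolled 45-patient pilot, and its one numerical success rule, 75% reporting the tool useful, does not depend on this interval.

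A simple parametric replacement is not a full cure either. With skewed change, a t interval on clinician means also misses 95%. It is not equivalent to a mixed model when clusters are unequal, and 45 patients cannot divide evenly among 10, 11 or 12 clinicians.

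None of this answers the missing criterion, the missing bootstrap specification or the unadjusted primary tests.

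**Conclusion.** The concern holds as a prespecification gap in a primary outcome. The named tests ignore a clustering that the plan itself recognises, and the clustered interval is not defined well enough for two analysts to obtain the same one. It does not show that the plan's interval will under-cover, because the interval is not yet determined.

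The coverage loss, about 5 points, is conditional on a percentile bootstrap over 10-12 clinicians but holds at any ICC. The type I error inflation is conditional on an ICC of about 0.1 or more for the change score. What is at stake is the calibration of preliminary data for a later trial. The gap merits correction because it is cheap to close.

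**What to change.** In Protocol 8.4 and 8.5, replace the conditional sentence with one prespecified clinician-clustered method, used for both the 95% interval and the primary p-value on the 1-15 change score. Either of these would serve:

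- a random-intercept model for the change score with Kenward-Roger degrees of freedom; or
- a bootstrap-t that resamples clinicians.

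Name one as primary and report the other as a sensitivity analysis. State that neither a percentile nor a patient-level bootstrap will be used. Keep signed-rank and exact McNemar as supportive. Write the same analysis into the SAP, which at present has no analysis of intention beyond description.

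The cost is a few sentences and a wider interval. Against the percentile bootstrap, a t(k−1) interval is wider by 1/0.853 = 1.17 at 12 clinicians, 1/0.839 = 1.19 at 11 and 1/0.822 = 1.22 at 10, so roughly a fifth. Neither recommended method is exact under strong skew or heavy ties with so few clinicians, and the report should say so.
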